## II. First Lanthanum Carbonate Medication

Time of First Exposure to Treatment (Lanthanum Carbonate) in either Part 2 or Part 3 of the study.

## III. Baseline Phosphate Level:

Procedural Steps:

- i) Obtain the baseline lab visit (from central lab) for each individual subject and choose the lab visit that is closest to the first lanthanum carbonate administration date; and
- ii) Obtain the baseline lab visit (from local lab, whenever available) for each individual subject and choose the lab visit that is closest to the first lanthanum carbonate administration date. This data will be used further when there is no central lab baseline Phosphate result (see below)l lab result.

## IV. Post 8-week Phosphate Level:

- i) Subset week 8 central lab data from Part 2 or Part 3 central lab data, selecting the on-treatment record closest to target day 56/week 8 (with +/-7 days window). Target day is created using the first dose of Lanthanum in Part 2 or Part 3 (if Part 2 first Lanthanum dose is missing).
- ii) Subset week 8 local lab data from Part 2 or Part 3 local lab data, select the on-treatment record closest to target day 56/week 8 (with +/-7 days window). Target day is created using the first dose of Lanthanum in Part 2 or Part 3 (if Part 2 first Lanthanum dose is missing).
- iii) For subjects who experienced hypophosphatemia, that lead to temporary interruption or discontinuation of treatment before the 8 weeks phosphate assessment they will be considered compliant with the 8 weeks treatment requirement.

In the case of missing central lab data, local lab data will be used. Serum phosphorous assessments must come from a homogeneous source ie, from either central or local lab for baseline and following weeks 8 of lanthanum treatment, respectively, within subject.

If baseline phosphorus value from central lab is available and above the KDOQI criteria, but the central lab 8-week value is missing, then local lab data (baseline and day 56/week 8 phosphorus results) can be used.

NB. Both the baseline and day 56/week 8 phosphorus results must come from a single source (both central or both local).

If baseline phosphorus value from central lab is available and not above the KDOQI criteria, then the subject is not evaluable even if the subject has local lab values for both baseline and 8-week and the baseline value satisfies KDOQI criteria. Evaluability based on local lab is assessed only if central laboratory data is missing.

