#### **7.1.1.3 Part 2b: Screening Visit (Visit 1.0; Week 0)**

The Investigator or designee will obtain written informed consent/assent from the subject/LAR prior to any study-related procedures being performed. Upon completion of Visit 1.0 for Part 2b, these subjects will enter Visit 2.1. All new eligible subjects will directly enter Part 2b under Version 6.0 of the protocol.

Each subject will be assigned a unique 7-digit number in the order that they present in the clinic, eg, the first subject at Site 001 would be 001-0001, the second 001-0002.

- All inclusion/exclusion criteria will be assessed and demographic characteristics recorded (Version 6.0 of the protocol).
  - Eligibility can be based on local laboratory results; however blood samples must be submitted to the central laboratory to obtain central laboratory results. Phosphorus levels and serum pregnancy results must be taken from samples within 7 days of planned enrollment, and PTH samples must be taken within 3 months of planned enrollment.
- Significant medical and renal history (in the Investigator's opinion) will be recorded, including the last assessment of glomerular filtration rate taken from the medical record.
- A full physical examination including height, weight, and vital signs will be performed.
- A 12-lead ECG will be undertaken to exclude any underlying cardiac diseases.
- Blood samples will be taken for biochemistry, hematology and biochemical bone markers.
- All females will undergo a serum pregnancy test.
- All concomitant medication and ongoing AEs will be recorded.
- Confirmation of dialysis adequacy and dietary advice will be made.
- Investigational product will be dispensed to subjects who have a level of serum phosphorus equal to or greater than the age appropriate KDOQI guidance (aged under 12 years: serum phosphorus >6.0mg/dL [1.94mmol/L] and aged 12 years and older: serum phosphorus >5.5mg/dL [1.78mmol/L]).
- If all criteria are met except the phosphate level, the subject will enter the washout period W1 for Part 2b.

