##### **Part 2a (between Visits 2.0 and 2.1) and Part 2b (between Visit 1.0 and 2.1)**

Subjects must stop taking any phosphate binder medication for up to 3 weeks prior to the first dose of investigational product if their phosphate levels are <6.0mg/dL (1.94mmol/L) for subjects under 12 years or <5.5mg/dL (1.78mmol/L) for subjects aged 12 years and over.

If a subject aged under 12 years already has phosphate levels >6.0mg/dL (1.94mmol/L) or >5.5mg/dL (1.78mmol/L) for subjects aged 12 years and older, the subject may proceed directly to the next part of the study (Visit 2.1). If a subject has started calcium carbonate or lanthanum carbonate based on local laboratory results, the subject will be allowed to continue in the study even if central laboratory results do not agree.

If phosphate levels reach >6.0mg/dL (1.94mmol/L) for subjects aged under 12 years or >5.5mg/dL (1.78mmol/L) for subjects aged 12 years and older during the washout, the subject will be withdrawn from washout and start the next part of the study (Visit 2.1).

Blood sample(s) will be taken locally during the washout period to ensure the phosphorus reaches the KDOQI required level. When reached, the phosphate level should be confirmed by taking a sample (between 0.1-0.7mL depending on each country's specific requirements) which will be analyzed by the central laboratory. However subjects can be enrolled based on the local laboratory result.

Any AEs or changes to concomitant medication will be recorded.

Subjects who have participated in Part 1 do not need to have a washout prior to entering Part 2 (not applicable to part 2b).

Subjects who have completed the washout (W1) and have phosphate levels equal to or greater than the age appropriate KDOQI guidance (serum phosphorus >6.0mg/dL [1.94mmol/L] for subjects aged under 12 years; >5.5mg/dL [1.78mmol/L] for subjects aged 12 years and older) will:

- Part 2a: Be dispensed calcium carbonate at either the dose taken by the subject prior to starting the study or at a dose determined by the Investigator for new subjects based on standard clinical practice.
- Part 2b: Be dispensed lanthanum carbonate with the starting total daily dose as 1500mg for all subjects. The total daily dose will be titrated 2-weekly, as appropriate, until the target serum phosphorus level is achieved, or until a maximum daily dose of 3000mg is reached.
- Have any AEs that occurred since the last visit recorded.

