## 21. APPENDIX

### 21.1 Evaluable Subject Determination Plan

#### 1. Definition of Evaluable Subject in Per-Protocol Analysis Set 2 for Primary Endpoint Assessment

For the purposes of the primary endpoint assessment, at least 32 subjects, who complete 8 weeks of treatment with lanthanum carbonate and are assessable for baseline and 8 weeks serum phosphate level, will be required. Approximately 65 subjects may be enrolled to acquire at least 32 evaluable subjects. In order to prevent over enrolment, subjects' evaluability status will be assessed and confirmation of achieving at least 32 evaluable subjects will be performed.

The criteria that subjects must meet to determine eligibility include:

- Aged 10 years to <18 years of age at the time of consent
- Confirmed serum phosphorus level drawn prior to commencing Lanthanum therapy in Part 2 or Part 3 of the clinical trial (Baseline Phosphorus)
  - Subjects who participated in Part 2a and received calcium carbonate, baseline serum phosphorus must be drawn after a washout period of up to 3 weeks
- Baseline serum phosphorus levels above KDOQI recommendations:
  - Age <12 years: Serum phosphorus >6.0mg/dL (1.94mmol/L)
  - Age ≥12 years and older: Serum phosphorus >5.5mg/dL (1.78mmol/L)
- Demonstration of 8 weeks of Lanthanum therapy
- Confirmed serum phosphorus level after 8 weeks of Lanthanum therapy
- Both baseline and 8 weeks serum phosphorus levels are assessed at the same lab (central or local lab)
- Subjects, who received lanthanum carbonate therapy in part 2 or part 3 but did not receive 8 weeks of continuous treatment because of temporary dose interruption due to hypophosphatemia (protocol Appendix 2: guidelines for phosphorus and calcium levels), will be considered evaluable, if they satisfy other criteria mentioned above (eg baseline phosphate > KDOQI target).

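### For Part 2b washout subjects with no central end-of-washout phosphate, the SAP baseline rule falls back on the pre-washout central value and can remove them from the primary analysis set

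*SAP*

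**What the plan says.** **Baseline rule.** SAP 21.1, 1.1, item III tells the programmer to take central laboratory data and "choose the lab visit that is closest to the first lanthanum carbonate administration date". It sets no condition that the sample follow washout. A post-washout condition does appear in SAP 21.1, section 1, but only for one group: "Subjects who participated in Part 2a and received calcium carbonate, baseline serum phosphorus must be drawn after a washout period of up to 3 weeks". Part 2b has no counterpart.

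**Consequence.** SAP 21.1, 1.1, item IV: "If baseline phosphorus value from central lab is available and not above the KDOQI criteria, then the subject is not evaluable". The same sentence goes on to say that qualifying local values do not change this, and the next one adds: "Evaluability based on local lab is assessed only if central laboratory data is missing". SAP 10.1 makes PP2 the primary analysis population.

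**Part 2b samples.** At Visit 1.0 eligibility may rest on local results, "however blood samples must be submitted to the central laboratory to obtain central laboratory results" (Protocol 7.1.1.3). The same section says: "If all criteria are met except the phosphate level, the subject will enter the washout period W1 for Part 2b". Protocol 7.1.1.4 says the end-of-washout level should be confirmed by a central sample, then adds: "However subjects can be enrolled based on the local laboratory result".

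**Same-laboratory rule.** SAP 10.1, 10.3 and 21.1 require a subject's baseline and Week 8 phosphate to come from the same source, both central or both local.

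**The concern.** A Part 2b subject who goes through W1 normally has two kinds of pre-dose phosphate: a Visit 1.0 value on the existing binder, and an end-of-washout value after the binder was stopped. Only the second describes the state in which lanthanum was started, and it is the one that qualified the subject. The SAP rule does not tell them apart. It asks only which central sample is nearest to the first dose.

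When the central W1 sample was taken and is usable, the rule picks it and nothing goes wrong. When it is missing, the nearest central value is the pre-washout one. A subject enrolled correctly under the protocol is then classed as not hyperphosphataemic at baseline and leaves PP2 and the count towards 32. The loss is selective, because it falls on subjects whose phosphate was controlled on their previous binder.

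**Working it through.** **Step 1. Where 32 comes from.** SAP 2.5 gives 80.6% as the probability of seeing at least one event with a true rate of 5%. Check: 1 − 0.95^32 = 0.806, which agrees. (The protocol's 35 gives 1 − 0.95^35 = 0.834, also as stated.) This figure concerns safety, and the safety sets have no baseline phosphate condition, so a PP2 exclusion does not alter it. Here 32 serves only as the PP2 target.

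**Step 2. Trace a Part 2b washout subject with no central W1 result.**
1. Visit 1.0: central biochemistry, including phosphorus, is scheduled (Protocol Table 3 and 7.2.3.5).
2. Phosphate is not above target, so the subject enters W1 and the binder is stopped for up to 3 weeks. The synopsis allows up to 5 weeks for screening with washout.
3. The local value rises above target and lanthanum is started on it, as the protocol permits.
4. SAP item III: the only scheduled pre-dose central value left is Visit 1.0, so it is selected.
5. SAP item IV: that value is available and, in the expected case, not above target. The subject is not evaluable, and local data are not consulted because central data are not missing.

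Step 5 has two limits. Entry to W1 can rest on a local result, so a discordant Visit 1.0 central value above target would keep the subject in. A value exactly at target is unresolved, because SAP 21.1, 1.2 accepts values at or above target while SAP 4.6 and section 17 require values above it.

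**Step 3. Would treating the old value as missing be enough?** No. The subject would move to local data, and the same-laboratory rule would then need a local Week 8 value. The SAP window is day 56 ± 7, that is day 49 to 63.

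| Part 2b visit | Days | In window? | Local phosphate scheduled? |
|---|---|---|---|
| 2.3 (Week 6 ± 3 days) | 39–45 | no | yes |
| 2.4 (Week 8 ± 3 days) | 53–59 | yes | no |
| 3.0 (Week 12 ± 1 week) | 77–91 | no | yes |

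On scheduled data the subject would still be excluded. The baseline rule and the same-laboratory rule must be amended together.

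**Step 4. Size.** The documents give neither the Part 2b share of PP2, nor the share needing W1, nor the share without a central W1 result. Expected loss = (Part 2b subjects otherwise evaluable) × (share needing W1) × (share without a central W1 result). Assume 50–90% and 5–20% for the two shares, so the multiplier runs from 0.5 × 0.05 = 0.025 to 0.9 × 0.20 = 0.18.
- If half of 32 are Part 2b (assumption): 16 × 0.025 = 0.4 to 16 × 0.18 = 2.9 subjects.
- If all 32 were Part 2b (ceiling): 0.8 to 5.8.

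One subject is 1/32 = 3.1% of the target.

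**Step 5. Effect on the estimate, as an illustration.** Suppose PP2 shows 16/32 = 50%, with an exact 95% interval of 31.9% to 68.1%. Adding back three excluded subjects gives 16/35 = 45.7% if none responded and 19/35 = 54.3% if all did. The shift is at most 4.3 points either way, well inside the interval.

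**The case against.** The strongest case against is that this is a missing-sample edge case. The central W1 confirmation is scheduled, the endpoint is descriptive and single-arm, the subject remains in the FAS version of the primary table (Table 3.1.1.2), and about 65 may be enrolled to reach 32 with evaluability tracked. The SAP also gives central results priority on purpose, and enrolment on a local result does not promise PP2 membership. All of this stands and limits the size. It does not justify the baseline chosen: priority for central data is a reason to prefer one laboratory's measurement of the same state, not a measurement made before washout. The SAP itself requires a post-washout baseline for Part 2a calcium carbonate subjects.

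One could read item III's reference to having no central baseline result as covering a missing W1 sample. The text does not say so, and a Visit 1.0 central value is a central pre-dose result.

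Three stronger readings are tempting but not supported:
- *That a sizeable number is lost.* Applying assumed shares to all 35 subjects gives 35 × 0.025 = 0.9 to 35 × 0.18 = 6.3. PP2 pools Part 2a and Part 2b, only Part 2b is exposed, and neither share is in the documents.
- *That the SAP breaches a 7-day limit on baseline samples.* The protocol's words are "Phosphorus levels and serum pregnancy results must be taken from samples within 7 days of planned enrollment". That is an eligibility rule tied to enrolment, not to first dose.
- *That the change-from-baseline tables will report a wrong change.* With illustrative values of 5.0 before washout, 6.8 after it and 5.2 mg/dL at Week 8, the pre-washout baseline gives +0.2 instead of −1.6. But if 6.8 is local and 5.2 central, SAP 10.3 does not allow −1.6 either. The detailed baseline description is in the TLG shells, Appendix 2, which was not available.

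**Conclusion.** The point holds for a defined group: Part 2b subjects who went through W1, have no usable central end-of-washout result, and whose Visit 1.0 central phosphate was not above target. For them the SAP's stated rules select a baseline from before washout and exclude the subject from the primary set. This is a stated rule giving the wrong baseline, not merely a missing detail.

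The number is unknown and probably small. The effect is on PP2 only. The loss is selective, but a reader should not infer a bias in either direction, because the documents do not allow its direction or size to be computed. The conclusion assumes that the TLG shells do not contain an overriding rule. That could not be checked, although SAP 4.6 assigns the PP2 detail to Section 21. It is worth correcting before database lock.

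**What to change.** 1. **SAP 21.1, section 1 and item III(i).** Extend the Part 2a post-washout condition to Part 2b. For a subject who went through W1, only a sample drawn at the end of washout counts as baseline, and a pre-washout central value is treated as missing. Subjects who needed no washout keep their Visit 1.0 value. Add no 7-day limit before first dose: screening without washout may last up to 2 weeks, so such a limit could discard valid central baselines.
2. **SAP 10.1 and 21.1, item IV.** State an exception to the same-laboratory rule for this case: the local end-of-washout value may establish phosphate above target for PP2 membership, and the central Week 8 value decides response. This is coherent because the primary endpoint compares Week 8 with a fixed threshold and does not use the difference from baseline.
3. **Change-from-baseline tables (SAP 10.3).** Do not use the pre-washout value as baseline. Set the change to missing under the same-laboratory rule, or show it flagged as mixed-source. Align the choice with the baseline description in the TLG shells, Appendix 2.

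The cost is SAP wording, with no new visit or sample. The downside is that a few PP2 subjects will have a local baseline and a central Week 8 value; listing them would make this visible.

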## 1.2 Data Sources for Assessment of Evaluability

Evaluability Assessment will be performed on the subject level analysis data set (one record per subject) created through the steps described in section V.

Evaluability is determined if the following conditions are met

1. If subject is not a screen failure
2. Baseline Phosphate data is not missing, and baseline phosphate is  $\geq$  KDOQI Target
3. Week 8 Phosphate data is not missing

OR

Phosphate value missing at Week 8, but early termination shows hypophosphatemia (Protocol Appendix 2: guidelines for phosphorus and calcium levels).

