## 9.5 Selection of Subjects to be Included in the Analyses

**Screened Set** – The set of subjects who have signed informed consent.

**Enrolled Set** – Subjects who have signed informed consent and have begun some study procedures (eg, dispensed investigational product, current drug has been withdrawn).

**Safety Analysis Set 1** – Enrolled subjects who have taken 1 dose of investigational product in Part 1 and who have completed at least 1 follow-up safety assessment.

**Safety Analysis Set 2** – Enrolled subjects who have taken 1 dose of investigational product in Part 2 or Part 3 and who have completed at least 1 follow-up safety assessment.

It is noted that safety assessments from the period when a subject is exposed to calcium carbonate will be summarized for calcium carbonate treatment. Safety assessments from the

period when a subject is exposed to lanthanum carbonate will be summarized for lanthanum carbonate treatment.

**Safety Completer Set (SCS)** – Subjects who receive at least 8 weeks of lanthanum carbonate treatment from either Part 2 or Part 3 of the study.

**Full Analysis Set (FAS)**–Subjects who have taken at least 1 dose of investigational product and who have at least 1 phosphate assessment during Part 2 or Part 3.

**Per-protocol Set 1 (PP1)** – Subjects in the Full Analysis Set who complete 8 weeks of calcium carbonate treatment followed by 8 weeks of lanthanum carbonate treatment and who have serum phosphate assessment data available to allow summarizing the percentage of subjects achieving age-specific KDOQI target. Only subjects who have serum phosphate levels equal to or above the age-specific KDOQI targets at study entry and between the calcium carbonate treatment and lanthanum carbonate treatment at Visit 2.4 will be included in this set.

**Per-protocol Set 2 (PP2)** – Subjects in the Full Analysis Set who complete 8 weeks of treatment with lanthanum carbonate and who have serum phosphate assessment data available to allow summarizing the percentage of subjects achieving age-specific KDOQI target. Subjects who have serum phosphate levels equal to or above the age-specific KDOQI targets prior to the start of lanthanum carbonate treatment will be included in this set.

**Pharmacokinetic Set 1** - Subjects in the Safety Analysis Set 1 for whom the primary pharmacokinetic data are considered sufficient and interpretable. Subjects in Part 1 who vomited may be excluded from Pharmacokinetic Set 1.

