#### **4.6 Per-protocol Set 2 (PP2)**

Per-protocol Set 2 is defined as subjects in the Full Analysis Set who complete 8 weeks of treatment with lanthanum carbonate and who have serum phosphate assessment data available to allow summarizing the percentage of subjects achieving age-specific KDOQI target. Subjects who have serum phosphate levels above the age-specific KDOQI targets prior to the start of lanthanum carbonate treatment will be included in this set. Further details are described in the Evaluable Subjects Determination Plan which can be found in Section 21.

Subjects who experienced hypophosphatemia, that lead to temporary interruption or discontinuation of treatment before the 8-week phosphate assessment, are considered compliant with the 8 week treatment requirement (as treatment dosed per-protocol, Section 6.2.1) and can thus be included in the PP2, PP1, and SCS analysis populations.

In previous versions of the protocol, a Per-protocol (PP) Set, defined as consisting "... of all Subjects in the FAS who complete Part 2 (ie, subjects who have a visit 2.8 serum phosphorus assessment) and do not have any pre-defined major protocol deviations that may affect the primary efficacy variable" was the only analysis set created to summarize efficacy endpoints. Following Protocol Version 6.0 (Amendment 5), two PP sets: PP1 and PP2 were defined.

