### 10.1 Primary Efficacy Endpoint(s) and Analysis

The primary efficacy variable for the study is the percentage of subjects achieving age specific KDOQI targets for serum phosphate level following 8 weeks of lanthanum carbonate treatment. The KDOQI serum phosphorus targets are defined as:

- Adolescents aged  $\geq 12$ - $<18$  years:  $\leq 5.5$ mg/dL (1.78mmol/L)
- Children aged 10 years - $<12$  years:  $\leq 6.0$ mg/dL (1.94mmol/L)

For the primary endpoint, the percentage of subjects achieving age-specific KDOQI targets for serum phosphate levels after 8 weeks of lanthanum carbonate treatment will be descriptively summarized and calculated along with an exact (Clopper-Pearson) 95% confidence interval. PP2 will be the primary analysis population and will be used for this descriptive summarization. Serum phosphate levels tested at a central laboratory will be used for the analysis. In the case of missing central laboratory data, local laboratory data will be used. Please note that serum phosphorous assessments must come from a homogeneous source ie, from either central or local laboratory for baseline and following weeks 8 of lanthanum treatment, respectively, within subject (**Table 3.1.1.1 and Table 3.1.1.2**). KDOQI Serum Phosphorous Target Achievement will be listed (**Listing 6.1**).

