- The age group categories that will be summarized for the “by Age” summary tables for Subject Disposition, Demographic and Baseline Characteristics and Adverse Events have been clarified and now explicitly align with the age groups upon which the primary and secondary endpoints are analysed (≥ 10 to <12 years and ≥12 to <18 years vs. <12 years and ≥12 years).
- The study will enrol at least 32 (rather than 35) subjects who complete 8 weeks of treatment with lanthanum carbonate and are assessable for the primary endpoint.
- The definitions of PP1 and PP2 will only include subjects who have serum phosphate levels above the age-specific KDOQI target (rather than equal to or above).

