#### 1.1 Data Variable Requirements

##### I. Subject Age

Age is calculated using Informed Consent Date minus Birth date. However, birth date may not be available in all cases (due to subject privacy concerns). When instead of birth date only birth year is entered in the clinical database, age will be imputed using June 30th of the year of birth. However, if the age falls below 10 years old or over 18 years old and inclusion criteria number 01 is met, we will consider the age-categories to confirm whether the age-criterion was met. KDOQI Target: Created based on age condition:

- If DM.AGE <12 years, then KDOQI Target = 1.94mmol/L
- If DM.AGE ≥12 years, then KDOQI Target = 1.78mmol/L

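### SAP 21.1, section 1.2, condition 2 counts a baseline phosphate exactly at target as evaluable for PP2, contrary to the strictly-above rule elsewhere in the SAP

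*SAP*

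**What the plan says.** SAP 21.1, section 1.2 gives three conditions to be applied to a dataset with one record per subject. The second is "Baseline Phosphate data is not missing, and baseline phosphate is $\geq$ KDOQI Target". The term KDOQI Target is defined a little earlier, in section 1.1 I: "If DM.AGE <12 years, then KDOQI Target = 1.94mmol/L", with 1.78 mmol/L for subjects aged 12 or older.

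The rest of the SAP states the PP2 baseline rule without equality:

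- SAP 4.6 includes "Subjects who have serum phosphate levels above the age-specific KDOQI targets prior to the start of lanthanum carbonate treatment".
- SAP 17, listing departures from the protocol, says of both per-protocol sets that they "will only include subjects who have serum phosphate levels above the age-specific KDOQI target (rather than equal to or above").
- SAP 21.1, section 1 writes both age-specific cut-offs with a > sign. Its allowance for interruptions due to hypophosphatemia applies to subjects "if they satisfy other criteria mentioned above (eg baseline phosphate > KDOQI target").
- SAP 21.1, section 1.1 IV says: "If baseline phosphorus value from central lab is available and not above the KDOQI criteria, then the subject is not evaluable".

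The protocol (section 9.5) had the wider rule: "Subjects who have serum phosphate levels equal to or above the age-specific KDOQI targets prior to the start of lanthanum carbonate treatment".

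SAP 10.1 fixes the role of the set: "PP2 will be the primary analysis population and will be used for this descriptive summarization". The endpoint there is success at or below target, so equality counts as success.

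**The concern.** Section 1.2 is the condition list for the subject-level dataset, so it is the text a programmer is most likely to code. If it is coded as written, a subject whose baseline equals the target enters the primary population although SAP 4.6 and SAP 17 exclude that subject. Such a subject satisfies the endpoint before the first dose of lanthanum carbonate and can count as a success with no fall in phosphate. The strict rule prevents this.

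The same list is used to confirm that at least 32 evaluable subjects have been reached, so a tied subject could also fill a place in that count.

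**Working it through.** **Which rule governs a tie.** Take a subject aged 12 or older with a baseline of exactly 1.78 mmol/L, or a younger subject at exactly 1.94 mmol/L.

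| Place in SAP | Baseline rule | Tied subject |
|---|---|---|
| 4.6 | above | out |
| 17 | above, equality removed | out |
| 21.1, section 1 | > cut-off | out |
| 21.1, section 1.1 IV (central baseline) | not above means not evaluable | out |
| 21.1, section 1.2, condition 2 | ≥ target | in |
| 10.1 endpoint applied to the baseline value | ≤ target | already a success |

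SAP 17 shows that the strict rule is intended. The ≥ agrees only with Protocol 9.5, which SAP 17 says it is changing.

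**Where the error can act.** With a central baseline, section 1.1 IV excludes the tied subject and section 1.2 includes the same subject, which is a direct contradiction. With local fallback, section 1.1 IV has no explicit exclusion of this kind, and only the general criteria in section 1 stand against condition 2.

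**The plan's own figure.** SAP 2.5 gives 80.6% as the probability of at least one event with 32 subjects and a true rate of 5%. Check: 1 − 0.95^32 = 0.806, which reproduces. If one of 32 counted subjects were a tie, 31 would be valid, and 1 − 0.95^31 = 0.796. However, removal from PP2 does not remove a treated subject from the safety sets, so the stated probability does not depend on this operator.

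**Size of the effect on the primary percentage.** Let p be the response proportion among 31 valid subjects, and add one tied subject.

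- Tied subject at target at week 8: (31p + 1)/32 − p = (1 − p)/32.
- Tied subject not at target at week 8: 31p/32 − p = −p/32.

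Neither shift can exceed 1/32 = 3.1 points. The response rates below are assumed for illustration; intervals are Clopper-Pearson 95%, as in SAP 10.1.

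| 31 valid subjects | plus one tie, at target | plus one tie, not at target |
|---|---|---|
| 15/31 = 48.4% (30.2 to 66.9) | 16/32 = 50.0% (31.9 to 68.1) | 15/32 = 46.9% (29.1 to 65.3) |
| 22/31 = 71.0% (52.0 to 85.8) | 23/32 = 71.9% (53.3 to 86.3) | 22/32 = 68.8% (50.0 to 83.9) |

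The shifts shown are 0.9 to 2.2 points. The interval at 16/32 is 68.1 − 31.9 = 36.2 points wide.

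**The case against.** Section 1.2 cannot be the whole rule. Its three conditions leave out age, eight weeks of therapy and the same-laboratory requirement, all of which section 1 makes mandatory. It can be read as presupposing section 1 and section 1.1 IV, and on that reading a central-laboratory tie is already excluded. Most subjects also had to exceed the same cut-offs to start treatment (Protocol 4.1, criterion 5), so ties should be rare. An exception is subjects who moved to Part 3 without reaching the level (Protocol 7.1.2.4). The analysis is descriptive, and the Full Analysis Set summary of the same endpoint (SAP Table 3.1.1.2) uses no baseline phosphate criterion.

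All of this stands and limits the weight of the point. It does not remove the contradiction: a list that says how evaluability is determined should not state a rule that the same document has withdrawn.

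A reader might go further and infer that the comparison unit is not fixed, because the cut-offs are led by mg/dL. With the protocol's pair of 10.0 mg/dL and 3.23 mmol/L (section 4.4.1), 1.78/0.323 = 5.51 mg/dL, which seems to pass a 5.5 mg/dL cut-off while tying at 1.78 mmol/L. The same arithmetic would seem to let a week-8 response change with the unit. The documents do not support this reading. Section 1.1 I sets the target variable in mmol/L, and SAP 21.1, section 1 and SAP 10.1 print the same 1.78 and 1.94 mmol/L beside the mg/dL values. The apparent conflict comes only from back-converting rounded figures. What remains is that no rounding rule was found, which is missing detail and may be covered in specifications kept outside the SAP.

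**Conclusion.** The point holds for the operator. Condition 2 in SAP 21.1, section 1.2 contradicts SAP 4.6, SAP 17 and two other parts of the same appendix, and it restores the protocol wording that SAP 17 replaced. Intent is clear from SAP 17, so the correction needs no new judgement.

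Severity is low. Only exact ties are affected. Each one, if admitted to make 32, moves the primary PP2 percentage by at most 3.1 points, in either direction, against an interval about 36 points wide at 50%. It could also decide whether the floor of 32 has been met. The exposure lies mainly in local-laboratory fallback baselines, since an explicit rule already blocks central ties.

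These sizes assume 31 valid subjects plus one tie. The documents do not show that any tied subject exists, so it would be wrong to infer that the primary result is known to be affected.

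**What to change.** In SAP 21.1, section 1.2, change condition 2 to require baseline phosphate > KDOQI Target, using the mmol/L values set in section 1.1 I. Apply it to both central and local baselines, then re-run the evaluable count toward 32.

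As a tidy-up in the same edit, correct the reference in section 1.2 to a section V: the numbered steps end at IV.

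The cost is one character, one cross-reference and a re-run. The count may fall by the number of ties found, if any. The sample-size statement and the Full Analysis Set summary do not change.
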